4.1 In-vitro studies

In vitro cultivation of intervertebral disc cells as a monolayer has been performed by several investigating groups^{18,26,27} using different media. It was reported, that intervertebral disc cells were able to proliferate *in vitro* and regained their chondrocyte-specific properties after contact with collagenous media. ^{28,29} This led to the assumption, that *in vitro* expanded intervertebral disc cells could be transplanted into the disc and perhaps integrated into pre-existing collagenous structures.

4.2 Pre-clinical studies

An early (circa 1999) pre-clinical study in a rodent model showed that transplantation of autologous nucleus pulposus cells that had been activated by co-culture with annulus fibrosus cells into degenerated discs in rabbits, delayed the formation of clusters of chondrocyte-like cells, the destruction of disc architecture, and the elaboration of type-II collagen. ³⁰ This early study has led to many more recent attempts, using improved techniques, different models, and both autologous and allogeneic cell lines, to prevent further disc degeneration subsequent to discectomy. Clearly the advantage of exposing naïve cells with full differentiation capacity to appropriate guidance towards a specific phenotype is the direction and dimension intended.

[name] and Meisel ³¹ in cooperation with the Emory Spine-Center in Decatur, Georgia (USA) removed intervertebral disc material (segment L1/L2, L3/L4) from 18 dogs while leaving segment L2/L3 unchanged. Subsequently, transplantation of cultured autologous disc-derived chondrocytes (ADCT) into the intervertebral disc (segment L3/L4) was performed to investigate the hypothesis that autologous disc chondrocytes could be used to repair damaged intervertebral disc. Comparisons between the untreated degenerated disc (L1/L2), the normal intervertebral disc (L2/L3), and the disc level that had received the ADCT transplantation (L3/L4) were conducted over a 12-month period. The transplanted cells were integrated into newly developed extracellular matrix, produced an extracellular matrix that displayed composition similar to normal intervertebral matrix, and when the disc heights were analyzed for variance according to treatment, a statistically significant correlation between transplanting cells and retention of disc height was achieved. A good correlation was found between the macropathological results and the x-ray and MRI results.

These results led to the conclusion that progression of degeneration of the lumbar disc after operation can be prevented by transplantation of *in vitro* cultivated disc-derived cells into the intervertebral space and that the MRI is a suitable non-invasive method for evaluation of the changes.

CONFIDENTIAL	Clinical Protocol	DATE	Р	age
		9Dec2019		
	mented Disc Regeneration in the $\underline{\mathbf{T}}$ reatment of the or without Intervertebral Disc Herniation –	WRITER TG, DB, PW	NO. 20	REV 6
VAST-001-017				

Further work elaborated the use of non-cultured cell lines, or adipose-derived regenerative cells, in repairing the intervertebral disc following partial discectomy in dogs.³² This study was designed to evaluate the safety and performance of adipose-derived regenerative cells (ADRCs) injected into the canine spine six weeks post discectomy to engraft in the vertebral discs, to stimulate disc matrix deposition, and to enhance recovery by delaying further disc degeneration as measured by imaging, macroscopic and microscopic techniques as well as molecular biology assessments of proteins. The study concluded that the treatment of intervertebral discs with ADRCs in hyaluronic acid is safe and effective in this canine model of intervertebral disc injury that mimics clinical patients undergoing discectomy after herniation. ADRC treated discs in this study closely resembled healthy control discs at 6 and 12 months based on pathology as well as based on measurement of matrix protein amounts. ADRCs remained viable over the 12-month study period and stimulated significant increases in aggrecan and type-II collagen, two critical components comprising a normal disc matrix.

4.3 Clinical studies

In the first clinical approach in man, 8 patients suffering from traumatically caused disc herniation were chosen for an individual treatment (unpublished data, Meisel, [name], et al.). All patients underwent a sequestrectomy. Protruded disc material or cells that were removed during discectomy were used for *in vitro* proliferation. Five of the 8 patients received an autologous transplantation of the proliferated disc derived cells 3 months after discectomy.

One aim of this pilot study was to prove that the disc that underwent discectomy was healed after 3 months therefore ensuring that the transplanted ADCTs would not pass out of the disc. This was confirmed by utilizing a standardized volume pressure measurement that is commonly used during chemonucleolysis.³³

As no statistical analysis was planned for these individual attempts, individual case control observations were performed in order to investigate the methodological and medical questions. After a mean duration of follow-up of 8.2 months (1 - 18 months), the 5 patients who received an ADCT transplant were completely free of complaints, working fulltime and had resumed sports activities. First analyses of the MRI data showed no decrease in intervertebral height, no disc desiccation and no degenerative changes of the adjacent vertebral endplates. These results correlate well with the results of the pre-clinical rodent model.

The promising results of this pilot study led to *EuroDISC*, a prospective, randomized, multicenter clinical trial designed to assess the long-term efficacy of ADCT in a broader population that was initiated in 2002. From that study, 109 patients were followed and an interim of the results summarized as follows:

CONFIDENTIAL	Clinical Protocol	DATE	P	age
		9Dec2019		
Patients with Low Back Pain with	mented Disc Regeneration in the Treatment of the or without Intervertebral Disc Herniation –	WRITER TG, DB, PW	NO. 21	REV 6
VAST-001-017				

- 1. The annulus had healed sufficiently 12 weeks after discectomy to allow for a successful transplant.
- 2. The transplant was achieved by a minimally invasive percutaneous injection.
- 3. Patients receiving cells had greater pain reduction.
- 4. Discs in patients receiving cells had a significant difference in fluid content.
- 5. Adjacent discs also demonstrated a difference in fluid content.

The results of the pre-clinical and clinical studies described above, provide the confidence that the transplant of ADCTs post-discectomy could be a viable treatment with long term effect and improvement over the standard of care.

CONFIDENTIAL	Clinical Protocol	DATE 9Dec2019	P	age
	mented Disc Regeneration in the T reatment of the or without Intervertebral Disc Herniation –	WRITER TG, DB, PW	NO. 22	REV 6

5 RATIONALE

Since 1991, several investigating groups have shown using *in vitro* and *in vivo* analyses, that degenerative changes of the intervertebral disc can be retarded, or positively influenced within the meaning of repair of the annulus fibrosus and the nucleus pulposus. ^{34,35} The clinical relevance of these investigations is still under discussion.

The aim of the VAST trial is to investigate the clinical relevance of the repair of intervertebral disc tissue by a supplementary transplantation of cellularized allograft disc matrix in a controlled clinical study, or continued treatment with conservative, non-surgical intervention. The clinical differences between the three groups will be compared by analyzing pain, functional restrictions and efficiencies of the lumbar spinal column, and neurological deficits using different scores that were especially developed for the assessment of degenerative back complaints. Additionally, X-ray and MRI will be performed in order to compare the morphologic changes between the active allograft treatment, placebo treatment and conservative care treatment groups. Evaluations of X-ray and MRI will include changes in the height of the intervertebral disc, modic changes of the adjacent endplates and the fluid content of the operated intervertebral disc.

The main target of this new method is to slow down the complex degeneration process of the intervertebral disc that often increases after operation of the disc and to offer prescriptive option to therapeutic intervention that is clinically relevant and economically efficient.⁴²

All previous and current human studies of transplanted cells, have involved the use of autologous or allogeneic cells that required *ex vivo* expansion of the cells, which is costly, time-consuming and strictly regulated, making it an intricate procedure. By utilizing allograft preparation technology refined by UMTB through minimal manipulation of the tissue and cells, strict regulatory issues are circumvented. Clinical costs may also be reduced, as the number and duration of hospital admissions may be diminished, and the need for expensive stem cell culture facilities is eliminated.

A variety of autologous ADRCs have been tested and are being utilized in a variety of indications in the clinic including breast reconstruction surgery subsequent to mastectomy, ^{43,44,45} cosmetic surgery of the face^{46,47} and breast, ⁴⁸ and both acute⁴⁹ and chronic⁵⁰ cardiovascular disease. While the mechanism of action remains to be fully elucidated, pre-clinical studies indicate that a variety of cells transplanted into the disc are capable of generating extracellular matrix and providing the necessary cellular components required to prevent further disc degeneration following discectomy. Cells aligned to this study and supplementary allograft material offer confidence in

CONFIDENTIAL	Clinical Protocol	DATE	Р	age
		9Dec2019		
	mented Disc Regeneration in the T reatment of th or without Intervertebral Disc Herniation –	WRITER TG, DB, PW	NO. 23	REV 6

differentiation towards a nucleus pulposus phenotype, therefore, it is warranted to conduct this study and to confirm this technology in a controlled, safe, and regulated environment.

To minimize patient risk, the first 24 patients (at least 4 from each group) will have an additional clinic visit one month after transplantation and will undergo a full safety assessment; including X-ray and MRI (see Appendix A). All data collected up to and including this point in the study will be collected and reviewed by the Steering Committee, who will determine if patient recruitment can continue. The parameters used by the Safety Committee to determine whether recruitment can continue, will be pre-defined in a separate document but will include the following:

- 1. A comparison of the adverse event (AE) profile between the three groups including rate, relationship, and severity.
- 2. A comparison of the clinical laboratory parameters between the three groups.
- 3. A comparison of vital signs and physical examination findings between the three groups.
- 4. A comparison of X-ray and MRI findings between the three groups.

CONFIDENTIAL	Clinical Protocol	DATE 9Dec2019	P	age
	mented Disc Regeneration in the $\underline{\mathbf{T}}$ reatment of th or without Intervertebral Disc Herniation –	WRITER TG, DB, PW	NO. 24	REV 6

6 STUDY DESIGN

This is a, prospective, randomized, parallel-arm, multicenter study that will enroll up to 220 evaluable patients at up to 20 clinical sites. The outcomes of this trial will be based on assessment of primary and secondary endpoints at 6 and 12 months after treatment of supplementary allograft compared to conservative care in subjects who have pain attributable to disc degeneration as judged by MRI scoring (Pfirrmann), physical examination, and patient reported pain. Optional long term follow up at 24 and 36 months for all randomized subjects will allow for additional secondary endpoints to analyze pain.

The study is composed of three phases – the Screening Phase (enrollment), Active Phase (12 months) and the optional follow up period (additional 24 months). As outlined in Figure 1, there is an indeterminate overlap of up to 14 days between the end of the Screening Phase and the start of the Active Phase for individual subjects in order to evaluate the protocol, and consent to their participation. After completing the Informed Consent procedure, screening and study specific procedures can be performed. Only patients that meet the entry criteria for both phases are eligible and can participate in this study.

During the 14 days of the Screening Phase (Day -14 to Day 0), patients will be assessed for study eligibility to establish their baseline condition, and will be randomized to either conservative care (maintaining current level of care), or be provided with supplementary allograft transplantation (Day 0 of the Screening Phase), or receive placebo treatment (saline). All patients who are randomized to conservative care in the Screening Phase (Day -14 to Day 0), will be evaluated as per standard of care and will be assessed along with those who are selected for eligibility to enter the Active Phase of allograft transplantation.

[figure not shown]
The first 24 subjects randomized (at least 4 subjects from each group) will return to the clinic for a safety assessment 1 month after treatment. Subsequent clinic visits will occur at 6 and 12 months following treatment for safety and efficacy assessments. Subjects randomized to conservative care will additionally receive a clinical follow-up at 3 months to assess pain, change, or loss of function since their initial visit.

Optional long term follow up at 24 and 36 months for all randomized subjects will allow for additional secondary endpoints to analyze pain. Subjects who wish to participate in the long term follow up will reconsent with the informed consent addendum 2 during an office visit. Subjects then will be reassessed for inclusion/exclusion criteria and fill out VASPI, ODI, SF-36, and Resource Utilization questionnaires. If eligible for an allograft injection, the PI will perform a neurological exam, physical exam, labs, and give the subject applicable questionnaires. An MRI and x-ray will be performed on subjects receiving another injection for safety purposes.

CONFIDENTIAL	Clinical Protocol	DATE 9Dec2019	P	age
	mented Disc Regeneration in the T reatment of th or without Intervertebral Disc Herniation –	WRITER TG, DB, PW	NO. 25	REV 6

The 36-month visit can be performed over the telephone by the study coordinator if the subject wishes.

Figure 1 – Study Design

6.1 Study Population

The study population will consist of approximately 220 male or female patients of any ethnicity from 18 to 60 years of age who demonstrate clinical disc degeneration at one or two vertebral level from L1 to S1 that would be considered candidates for conservative care, or surgery. Patients must be classified with moderate to severe disability (ODI ≥40%) and chronic pain (VASPI ≥40 mm). Eligible patients must have no contraindications to allograft transplantation, have a life expectancy of >2 years, and be willing to return to the clinic for multiple safety and efficacy assessments for up to 12 months following enrollment.

6.2 Patient Identification and Randomization

The Informed Consent Form (ICF), signed prior to any study specific screening procedures being completed, will provide details on both the Screening Phase and the Active Phase of the study. Each patient that signs Informed Consent will be randomized to the active allograft, placebo, or conservative care treatment group. The randomization will occur through a secured envelope system, during which the subject will be provided with a unique subject identification number (XX-XXX, site number-subject number). During the Screening Phase, all subjects randomized to active allograft or placebo treatment will be scheduled for a transplantation procedure, while the conservative care treatment subjects will be followed as per the routine standard of care.

CONFIDENTIAL	Clinical Protocol	DATE	Р	age
		9Dec2019		
Patients with Low Back Pain with	mented Disc Regeneration in the $\underline{\mathbf{T}}$ reatment of the or without Intervertebral Disc Herniation –	WRITER TG, DB, PW	NO. 26	REV 6
VAST-001-017				

On or before Day 0 of the Active Phase, the patency of the affected disc will be confirmed, and subjects determined eligible from the screening phase who have consented to participation and are randomized to allograft treatment will receive the study material. Patients are considered enrolled in the study when they undergo successful treatment in the Active Phase and receive either allograft treatment, placebo (saline) treatment, or conservative care treatment.

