During the Screening Phase, subjects will be assessed for study eligibility, X-ray and MRI within the previous 6 months, SF-36, ODI, and VASPI to establish a baseline for participation. If meeting eligibility, they will be scheduled for allograft treatment, placebo (saline) treatment, or conservative care treatment. Those who meet the Active Phase entry criteria will be randomized at Day 0 to either receive the viable allograft, placebo as saline, or be assigned to continue conservative treatment. Specified subjects, as noted below, will return to the clinic for a safety assessment 1 month after the transplant, and subsequently at 6, and 12 months for safety and efficacy assessments. Patients who continue conservative care will be evaluated at 3 months, as well as 6 and 12 months. Physicians at their discretion can bring subjects back for follow-up to assure safety at any time point throughout the duration of the study. The first 24 patients to be randomized (at least 4 from each treatment group) will have an additional study visit 1 month after treatment. All data from the 1-month study visit will be collected and reviewed by the Steering Committee to confirm that enrollment can continue. Subjects will have the option to continue with a long-term follow up at time points of 24 and 36 months. Questionnaires will be completed over the phone with the study coordinator's prompting or during an in-office visit. All randomized subjects will also have the option to receive an allograft injection during the 24 month office visit after meeting inclusion/exclusion criteria. Able to provide an English written Informed Consent **Inclusion Criteria** • Age 18 to 60 years inclusive • Male or female Body mass index <35 Pfirrmann Grade [3-6]

CONFIDENTIAL	Clinical Protocol	DATE 9Dec2019	P	age
	mented Disc Regeneration in the $\underline{\mathbf{T}}$ reatment of th or without Intervertebral Disc Herniation –	WRITER TG, DB, PW	NO. 13	REV 6

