6.3 Blinding

The assignment to treatment (active allograft, or placebo, or conservative care) is open label at Day 0 of the Active Phase to the extent that subjects receiving allograft or placebo will not be aware of what they have received, while those assigned to conservative care will be aware. All site study staff will be aware of the group to which each subject is randomized. Sites will be trained to ensure that subjects receiving the allograft or placebo treatment will remain blinded to their treatment throughout the study duration. Subjects will be unblinded during the study exit or upon signing of the new informed consent for the study extension.

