6.10 Subject Withdrawal and Replacement

Subjects may withdraw from the study at any time without penalty and for any reason without prejudice to their future medical care. In all cases, the reason(s) for withdrawal, and the primary reason, must be recorded on the appropriate case report form (CRF). If a subject is prematurely withdrawn from the study after randomization (Day 0 of the Active Phase), the investigator must document the reason(s) and make every effort to perform a final Termination Visit. The procedures to be followed for the Termination Visit are the same as those defined for the Month 12 Visit.

Subjects that are consented, screened and randomized, but do not undergo a successful transplantation (Day 0 of the Active Phase) will be considered screen failures. These randomization assignments will be re-used. The randomization and the replacement of subjects will be orchestrated through a 3rd party designated independent of the data collection or analysis.

CONFIDENTIAL	Clinical Protocol	DATE	Р	age
		9Dec2019		
Patients with Low Back Pain with	mented Disc Regeneration in the $\underline{\mathbf{T}}$ reatment of th or without Intervertebral Disc Herniation –	WRITER TG, DB, PW	NO. 29	REV 6
VAST-001-017				

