8.5 Assessments

- Informed Consent will be obtained between Screening Day -14 and Active Day 0, prior to any study procedures being performed. The addendum for optional long term follow up will be collected before procedure and questionnaires are performed.
- An assessment of eligibility using the inclusion and exclusion criteria will be conducted starting at Day -14 of the Screening Phase. Prior to randomization at Day 0 of the Screening Phase, eligible subjects must meet all inclusion criteria and no exclusion criteria for the Active Phase. This will also be assessed after the ICF addendum for long term follow up is collected to determine if the subject is still eligible.
- Medical History and Patient Demographics will be recorded during the Screening Phase.
- An abbreviated Physical Examination will be done in the Screening Phase within the 2 weeks prior to transplant, as well as at Month 6, and 12, and at 3 months for the subjects randomized to continue conservative care. This will be done for subjects completing the placebo crossover injection as well.
- Resource utilization data (lost time from work, number and kind of previous surgeries, duration of complaints (preoperatively), duration of rehabilitation, complications, additional physician visits, etc.), will be obtained during the Screening Phase as a baseline to similar data obtained during the Active Phase at Months 6, and 12. This will also be collected during the long term follow up visits of 24 and 36 months.
- Physicians clinical assessments will be collected in the Screening and in the 2 weeks prior to transplant, and in the Active Phase at Months 6, and 12, and in the conservative

CONFIDENTIAL	Clinical Protocol	DATE	Р	age
		9Dec2019		
	mented Disc Regeneration in the $\underline{\mathbf{T}}$ reatment of th or without Intervertebral Disc Herniation –	WRITER TG, DB, PW	NO. 37	REV 6

- care patients at 3, 6, and 12 months. A neurological exam will be completed before placebo crossover additionally.
- Patient self-assessments including VASPI, ODI, and SF-36 will be collected at every scheduled clinic visit. VASPI, ODI, and SF-36 will be collected in person at 24 months and at the 36 month interval, these questionnaires can be performed over the phone during optional long term follow up.

CONFIDENTIAL	Clinical Protocol	DATE	Р	age
		9Dec2019		

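### Protocol 6.2 randomises consenting patients without an eligibility condition while other sections randomise only after eligibility; if sites follow 6.2, unblinded staff could judge eligibility knowing the arm

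*Protocol*

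**What the plan says.** Protocol 6.2 has consent "signed prior to any study specific screening procedures being completed" and then says "Each patient that signs Informed Consent will be randomized to the active allograft, placebo, or conservative care treatment group". It continues: "During the Screening Phase, all subjects randomized to active allograft or placebo treatment will be scheduled for a transplantation procedure". Eligibility appears in 6.2 as a condition for receiving the study material, not for being allocated. Section 6 also places randomisation within Day -14 to Day 0, alongside the eligibility assessment, without giving their order.

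Other places give a different order. The synopsis says: "Those who meet the Active Phase entry criteria will be randomized at Day 0". Section 8.5 says: "Prior to randomization at Day 0 of the Screening Phase, eligible subjects must meet all inclusion criteria and no exclusion criteria for the Active Phase". Appendix A marks randomisation at the Day 0 visit (VA1), with the main eligibility work at screening (VS1). The Study Design entry in SAP section 2 randomises those who have met both the screening and the Active Phase criteria.

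On knowledge of the arm, section 6.3 says: "All site study staff will be aware of the group to which each subject is randomized". On subjects randomised without a successful transplantation, section 6.10 says they "will be considered screen failures. These randomization assignments will be re-used".

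**The concern.** A site cannot work to both orders. Section 6.2 carries the randomisation title and is the only section that describes the envelope system, so a coordinator could reasonably take it as the working instruction.

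If allocation comes first, eligibility is settled by people who know the arm. Some criteria in 8.1 and 8.2 rest on judgement, such as the ability to comply and other severe disease as the investigator sees it. Exclusions could then differ by arm for reasons related to prognosis. That is selection bias after allocation, and the planned analysis sets would not contain the patients needed to assess it.

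**Working it through.** The plan gives no figure on this point, so there is none to reproduce. The check is mainly a reading of the text, followed by an illustration of size.

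**1. Order of events**
- Section 6.2: consent, then allocation of each consenting patient. Arm-specific booking takes place during screening, and treatment goes to those found eligible.
- Section 6: eligibility assessment and randomisation both within Day -14 to Day 0, order not given.
- Synopsis, 8.5, Appendix A and SAP section 2: eligibility first, then randomisation.
- Section 6.10 equates randomisation with Day 0 of the Active Phase.
- Section 7.1.2 is mixed. It requires the criteria still to be met at Day 0, but describes disc patency being confirmed for subjects already randomised to allograft or placebo. Disc confirmation is an inclusion criterion in 8.1. As written, part of eligibility may therefore be checked after allocation, and in the injection arms only.

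**2. Who knows the arm**
All site staff do (6.3). No section says that eligibility is locked before the envelope is opened, or judged by someone unaware of the arm.

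**3. Where an excluded patient goes**
The SAP's ITT set requires confirmed eligibility, not randomisation (SAP 6.1). The mITT and safety sets are drawn from ITT, and PP from mITT (SAP 6.2-6.4). A patient found ineligible after allocation is therefore in none of them. SAP 7.2 accounts for everyone who consented in the CONSORT diagram, which gives a count but no outcome.

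**4. Illustration of size**
Inputs from the documents: SD 15.5 (Protocol 13.3), arms of 140, 40 and 40 (synopsis), Kruskal-Wallis at two-sided 0.05 with both ODI and VASPI significant (SAP 7.5, 9.1).

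Assumptions: a fraction f of allograft patients, those judged worst, is dropped and replaced; the judgement correlates 0.5 with outcome; there is no treatment effect; ODI and VASPI correlate 0.5-0.7.

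Shift in allograft mean = 0.5 x 15.5 x φ(z_f)/(1 - f):
- f = 0.10: z = -1.28, φ = 0.1755; 7.75 x 0.1755/0.90 = 1.5 points.
- f = 0.20: z = -0.84, φ = 0.2800; 7.75 x 0.2800/0.80 = 2.7 points.

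Against the planned 9-point difference, these are 1.5/9 = 17% and 2.7/9 = 30%.

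One endpoint, allograft against placebo: the standard error is 15.5 x √(1/140 + 1/40) = 2.78, or 2.84 after the rank-test factor √(π/3). The shifts are 0.53 and 0.95 standard errors. The two-sided false-positive rate, Φ(-1.96 + d) + Φ(-1.96 - d), is about 8% and 16%. Simulating the three-group Kruskal-Wallis test on one endpoint gives about 9% and 17-18%.

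Simulated false trial success, both endpoints significant:

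| Allograft patients dropped | False success |
|---|---|
| none | about 1-2% |
| 10% | about 2-3% |
| 20% | about 7-9% |

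**The case against.** The strongest reply is that 6.2 is loose drafting. The synopsis, 8.5, 6.10, Appendix A and the SAP all point to Day 0 or to eligibility first. Appendix A allows screening and Day 0 to fall on the same day, so there may be no interval at all. A third party independent of data collection and analysis also handles randomisation and replacement (6.10).

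Much of this stands. A reader might infer from 6.2 that the envelope is opened at the moment of consent, with eligibility decided over the following two weeks. The documents do not support that: 6.2 never gives the moment, and 14 days is a maximum. What survives is that 6.2 sets no eligibility condition on allocation and has the arm known during screening, which conflicts with the other sections. The third party does not help here, because it does not blind the site staff who assess eligibility.

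A reader might also take the 8-18% single-endpoint rate as the trial's error rate. It is not, because success requires both endpoints. At 10% dropped, false success stays below 5%. The scenario also drops allograft patients only. If placebo patients were dropped equally, the allograft-placebo comparison would stay at about 5%, though comparisons with conservative care would still be affected.

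Nor is the loss wholly invisible, since the CONSORT diagram counts these patients.

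**Conclusion.** The contradiction is real and should be resolved. Its consequence is conditional: if sites follow 6.2, eligibility can be judged with the arm known, and those excluded leave every analysis set. Nothing in the documents shows that biased exclusion took place, and most of the text already supports the safer order.

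The size cannot be derived from the documents. The 10-20% dropping, the 0.5 correlation with outcome and the 0.5-0.7 correlation between endpoints are all assumptions. Under them the allograft mean is biased by 1.5-2.7 points. False trial success rises from about 1-2% to 2-3% or 7-9%. The biased estimate matters even where the trial-level error rate stays under 5%. The point itself does not depend on these figures.

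**What to change.** - Replace the randomisation sentence in Protocol 6.2 with: *Subjects are randomised at Day 0, only after all inclusion and exclusion criteria have been confirmed and recorded; the envelope is opened last.*
- Reword the Screening Phase text in 6.2 and section 6 so that allocation follows confirmed eligibility. Striking out the word for randomisation is not enough: the section 6 sentences would no longer parse, and 8.5 itself speaks of randomisation at Day 0 of the Screening Phase.
- Reconcile 7.1.2 with 8.1, so that any disc confirmation counted as an eligibility criterion is recorded before allocation.
- Where subjects have already been randomised, state which order sites followed, and show in the CONSORT diagram, by allocated arm, those dropped between allocation and treatment.

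The cost is small. The changes to 6 and 6.2 are wording that follows the rule already in the synopsis, 8.5, Appendix A and the SAP, with no change to sample size. Reconciling the disc check needs a decision on when it is done and recorded. The practical downside is that the injection slot has to be booked before the arm is known.
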